2.2 Ethics

This study will be submitted to a central IRB for approval to begin research and study oversight.

Informed consent will be conducted by a member of the research team. When possible, a copy of the consent will be provided to the study candidate prior to the clinic visit. At the first clinic visit, a private room will be used to review the consent with the candidate and to answer any questions or concerns they may have regarding participation in the research study.

2.3 Device Description

2.3.1 Flexitouch Plus

The Flexitouch Plus (Tactile Medical™, Minneapolis, MN, USA) is a segmental, programmable, gradient advanced pneumatic compression device cleared for market in the USA (K170216, HCPCS code E0652). The device stimulates the lymphatic system by directing and moving excess fluid from an impaired lymphatic region to healthy regions where fluid can be absorbed and processed naturally by the body.

The system consists of two primary components: a controller unit and garments. The controller unit has connector outlets for garment hoses to plug into such that air can pass through the hoses and deliver treatment through sequential inflation and deflation of air chambers within the garments. The garments are constructed of nylon and have 27-32 chambers, depending upon garment size. The pressure setting is variable between “decreased,” “normal,” and “increased.”

The device is intended to provide in-home Manual Lymphatic Drainage (MLD) therapy for approximately 1 hour treatment duration. Indications for use include lymphedema, primary lymphedema, post-mastectomy edema, edema following trauma and sports injuries, post immobilization edema,

venous insufficiency, reducing wound healing time, and treatment and assistance in healing stasis dermatitis, venous stasis ulcers, or arterial and diabetic leg ulcers.

2.3.2 Conservative Care

Standard care for patients under the Principal Investigator's care includes 30-40 mmHg graduated compression up to waist, dietary counseling, exercise, and a referral for Complete Decongestive Therapy (CDT). Based on each patient's situation (e.g., insurance coverage, willingness/ability to independently comply with care, time constraints, etc.), some or all of these recommendations are typically followed. In this "real-world" study, no attempt is being made to control what will or won't be used in terms of conservative care since it varies in clinic practice for each patient.

3.0 Study Objective

The primary objective of the study is to assess the effectiveness of bilateral Flexitouch Plus use with conservative care based upon:

- Circumferential measurements at ankle, mid-calf, lower thigh, upper thigh, hip, and waist,
- Quality of life (RAND 36-Item Health Survey 1.0), and
- Patient-reported symptoms and pain intensity (PROMIS Pain Interference – Short Form 6b, Wong-Baker Faces Scale, and the NIH Toolbox numerical rating scale (NRS)).

Exploratory endpoints include:

- Mobility (PROMIS Mobility v2.0), and
- Bioimpedance measurements (Whole Body and Segmental Extracellular Water/Total Body Water (ECW/TBW) ratios using InBody 770).
- Comparing all objectives and endpoints between treatment groups.

4.0 Study Design

This is a prospective, randomized, two-arm study comparing Flexitouch Plus with conservative care to conservative care alone (Figure 1). This post-market study involves on label use of the Flexitouch Plus device given eligible patients must have concurrent diagnosis with lymphedema (as noted by Stage 2/3 lipedema with presence of secondary swelling upon physical exam) and obtain the device through normal commercial means (self-pay, patient assistance, or insurance programs).

[figure not shown]

Figure 1. Study Design

4.1 Endpoint Mapping

Endpoint	Outcome Measure	Analysis
Primary	
 Circumferential Measurements 	
 Calculate percent reduction at Follow-up compared to Baseline for 6 sites on each leg as well as a composite total.
Primary	
 Quality of Life 	
 Compare Follow-up RAND SF36 score to Baseline.¹
Primary	
 Symptoms & Pain Intensity 	
 Compare Follow-up PROMIS Pain Interference², Wong-Baker Faces Scale, and the NIH Toolbox numerical rating scale (NRS) scores to Baseline.
Exploratory	
 Mobility 	
 Compare Follow-up PROMIS Mobility score to Baseline.²

¹ https://www.rand.org/health-care/surveys_tools/mos/36-item-short-form/scoring.html

² http://www.healthmeasures.net/index.php?option=com_instruments&task=Search.pagination&Itemid=992

Endpoint	Outcome Measure	Analysis
Exploratory	
 • Bioimpedance Measurements 	
 • Calculate mean reduction at Follow-up compared to Baseline for the Segmental (Right/Left Arm/Leg, Trunk) and Whole Body Extracellular Water (ECW)/Total Body Water (TBW) ratios.

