6.7 Circumferential Measurements

Circumferential measurements will be taken at Baseline and Follow-up per standard care at the beginning of the visit at 4 sites on each leg (immediately after bioimpedance measurements and the removal of graduated compression), 1 site at the hips, and 1 site at the waist (for a total of 10 measurements) using a Gulick II tape measure. Sites include:

- Site 1=narrowest part of the ankle (right and left leg),
- Site 2=largest part of the calf (right and left leg),
- Site 3=top of knee cap for lower thigh (right and left leg),
- Site 4=thickest part of the upper thigh (right and left leg),
- Site 5=widest part of the hips, and
- Site 6=narrowest part of the waist.

Results will be recorded in centimeters on the respective data collection form.

At the Follow-up visit, additional circumferential measurements (including 4 sites on each leg, 1 site at the hips, and 1 site at the waist using a Gulick II tape measure) may be collected immediately after an approximately 60-minute in-clinic treatment with FT Plus. The measurements will be collected and recorded in the same fashion outlined above. .

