13.0 Statistical Methods

13.1 Sample Size Determination

The study is not formally powered for a specific primary hypothesis, thus no formal power/sample size estimation was performed. The study sample size was determined based upon a desire to be able to estimate the means of the primary within group endpoints, using 95% confidence intervals, with the estimation of the endpoint means to have a precision (half width of the confidence intervals) of approximately 40% of the observed standard deviation. To achieve these parameters, we have determined a target analyzable sample size of 15 subjects (30 total legs as the observational units) per group. To accommodate an expected attrition rate of up to 20%, a total of 3 subjects per arm will be replaced, if they fail to fully complete the study.

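### The primary girth endpoint is defined on six sites per leg, but four per leg plus one hip and one waist are measured, and the composite has no formula

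*Combined protocol and SAP*

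**What the plan says.** Section 3.0 places girth in the primary objective and names six locations: "Circumferential measurements at ankle, mid-calf, lower thigh, upper thigh, hip, and waist". Section 4.1 turns this into an analysis: "Calculate percent reduction at Follow-up compared to Baseline for 6 sites on each leg as well as a composite total". It does not say whether the composite is a sum or a mean, how many terms it has, or whether it is formed per leg or per woman. No other section says so either.

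Section 6.7 describes what is measured. Tape readings are taken "at the beginning of the visit at 4 sites on each leg", with "1 site at the hips, and 1 site at the waist (for a total of 10 measurements) using a Gulick II tape measure". Sites 1 to 4 are marked right and left. The last two are not: "Site 5=widest part of the hips" and "Site 6=narrowest part of the waist". Sections 6.7 and 6.10 repeat the same scheme of four per leg, one hip and one waist for the optional measurements after an in-clinic treatment.

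Section 13.1 sets the target at "15 subjects (30 total legs as the observational units) per group", chosen so that the 95% confidence interval for a within-group mean has a half-width of roughly 40% of the standard deviation.

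**The concern.** The endpoint definition and the measurement procedure disagree on how many values a woman contributes, and this is a primary endpoint. A programmer working from section 4.1, with the leg as the unit from section 13.1, would need six values for each leg and would find four. The only readings that could fill the gap are the single hip and waist values, used once for each leg.

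Two things would follow. Hips and waist are not leg measurements, yet they would carry double weight in the composite. And 15 readings per arm would appear in the dataset as 30, which makes the interval for those sites look narrower than it is. This differs from the general question of treating a woman's two legs as independent. A left and a right calf are two correlated measurements, whereas a copied waist is one measurement entered twice.

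Even if nobody copies anything, the composite can be built in several ways from the same data, and the choice is left until after the data are seen.

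**Working it through.** **Count of measurements.** Section 6.7: 4 sites × 2 legs + 1 hip + 1 waist = 10, which reproduces its stated total. Section 4.1: 6 sites × 2 legs = 12. The excess of 2 equals one extra hip and one extra waist.

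**Precision.** The half-width of a 95% interval for a mean, in SD units, is t(0.975, n − 1)/√n, or 1.96/√n with the normal quantile.

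- The plan's own figure, n = 30 legs: 0.373 with t, 0.358 with the normal quantile. Both are consistent with the roughly 0.40 SD in section 13.1.
- n = 15 women: 0.554 with t, 0.506 with the normal quantile.

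Hips and waist have one reading per woman per visit, so n is 15 per arm. The same holds for a composite that combines both legs with hips and waist, since it has one value per woman. Duplicating 15 values to make 30 barely changes the computed SD (factor √(28/29) = 0.983), so the displayed half-width would be close to 0.373/0.554 = 0.67 of the correct one. This step needs no assumed girths.

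**Weight in the composite.** As a mean of site percentages, hips and waist are 2 of 10 terms (20%) if counted once and 4 of 12 (33%) if counted twice. For a sum of centimetres girths are needed, and the documents give none. Assumed central values are 386 cm for the eight leg sites together and 225 cm for hips plus waist. The share is then 225/611 = 37% counted once and 450/836 = 54% counted twice.

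**Direction of the effect.** Assume a 3% reduction at every leg site (also not in the documents) and vary the trunk change. The ratio of sums is (386 × 0.03 + k × 225 × trunk change)/(386 + k × 225), with k = 1 for 10 terms and k = 2 for 12.

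| Trunk change | 8 leg sites | 10 terms | 12 terms |
|---|---|---|---|
| 0% | 3.0% | 11.58/611 = 1.9% | 11.58/836 = 1.4% |
| 1% | 3.0% | 13.83/611 = 2.3% | 16.08/836 = 1.9% |
| 3% | 3.0% | 3.0% | 3.0% |
| 4% | 3.0% | 20.58/611 = 3.4% | 29.58/836 = 3.5% |

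As a mean of site percentages, the 0% row reads 3.0%, 2.4% and 2.0%, and the 4% row 3.0%, 3.2% and 3.3%.

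Over a wider assumed range (leg sites 340 to 440 cm, hips plus waist 200 to 270 cm) with no trunk change, the 12-term result is between 610/880 = 0.693 and 640/840 = 0.762 of the 10-term result, so 24% to 31% smaller. That is the part due to double counting. The step from 8 to 10 terms comes from including hips and waist at all, which section 3.0 plans.

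**The case against.** The strongest reply is that section 4.1 is loose shorthand for Sites 1 to 6. The operational text treats hips and waist as single readings throughout, section 6.8 also speaks of Sites 1 to 6, and a total of the 10 recorded values is at least as natural as a 12-term sum. This stands. A reader might infer that the plan counts hips and waist twice. The documents do not say so, because no composite formula exists; duplication is only what a literal per-leg reading would require.

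A reader might also infer that any leg effect would be diluted. That does not hold in general. It requires the trunk to shrink proportionally less than the legs. The standard program in section 6.10 covers the core as well as the legs, and section 2.1 notes that the disease can reach the abdomen, so zero trunk change cannot be assumed. With equal change there is no shift, and with a larger trunk change the composite is raised.

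It is also fair to say that the consequence is limited. Section 4.1 asks for each site separately, so leg results stay visible, and sections 13.1 and 13.2 describe an unpowered study focused on estimation. But estimation is where the precision matters, and the shortfall for once-per-woman outcomes remains even if nothing is duplicated.

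**Conclusion.** The site count in a primary endpoint is wrong as written, and its composite is undefined. Both follow from the text alone. Hips, waist and any per-woman composite have 15 values per arm at the target size, so their expected 95% half-width is about 0.55 SD, not the planned 0.40 SD or so. This rests only on the target of 15 analysable women per arm and the usual t interval.

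The falsely narrow 0.373 SD and the double weighting are conditional on the single hip and waist readings being entered once per leg, which the plan permits but does not state. The composite then moves toward the trunk's change, in a direction that the documents do not settle. The percentages for that shift rest on assumed girths and changes and serve as illustration only.

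**What to change.** Reword section 4.1 to match section 6.7: *percent reduction at 4 sites on each leg, at the hips and at the waist (10 measurements), and for a composite in which each measurement counts once*. State whether the composite is a ratio of summed centimetres or a mean of site percentages. Specify that hips, waist and the composite are analysed with the woman as the unit (n = 15 per arm), and restate in section 13.1 their expected half-width as about 0.55 SD.

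The cost is an edit to the protocol and SAP text before analysis. It needs no new data, no change to the visits and no change to the sample size. A legs-only composite of the 8 leg sites, reported beside the main one, would help interpretation but is optional.

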4.2 Subject Selection

The target population includes patients who have bilateral lipedema, meet the criteria listed below, and have provided informed consent.

4.2.1 Inclusion Criteria:

1. Female age 18-70 years.
2. Stage 2-3 (Schmeller Type 2-3) lipedema with secondary lymphedema.
3. Willing and able to follow prescribed care for study period.
4. Able to access (via self-pay, patient assistance, or insurance programs) prescribed care within 60 days of Baseline visit.

4.2.2 Exclusion Criteria:

1. BMI > 50.
2. Heart failure (acute pulmonary edema, decompensated acute heart failure).
3. Pacemaker or implantable cardioverter defibrillator (ICD).
4. Acute venous disease (acute thrombophlebitis, acute deep venous thrombosis, acute pulmonary embolism).
5. Severe peripheral artery disease (critical limb ischemia including ischemic rest pain, arterial wounds, or gangrene).
6. Active skin or limb infection/inflammatory disease (acute cellulitis, other uncontrolled skin or untreated inflammatory skin disease) on the arms or trunk.
7. Active cancer (cancer that is currently under treatment, but not yet in remission).
8. Poorly controlled kidney disease (glomerular filtration rate < 30 mls per minute), hypoproteinemia, pulmonary hypertension, hypothyroidism, cyclic edema, or Munchausen Syndrome.
9. Any circumstance where increased lymphatic or venous return is undesirable.

10. Currently pregnant or trying to become pregnant.

4.3 Point of Enrollment

Subjects will be considered enrolled in the study once the Informed Consent Form is signed and eligibility criteria are met. The investigator will keep a record, or subject screening log, of subjects who enter screening. Any subjects who do not meet inclusion/exclusion criteria will be considered screen failures.

4.4 Treatment Assignment and Duration

Eligible patients will be randomized (1:1) using sealed envelopes to one of the following treatment cohorts:

- Conservative care alone (may include 30-40 mmHg graduated compression up to waist, dietary counseling, exercise, and/or referral for CDT); or
- Flexitouch Plus with conservative care.

Following randomization, a product demo may take place to confirm the subject is able to tolerate prescribed care.

4.5 Study Timeline

The expected study duration is approximately 24 months with 1 month spent in activation, 21 months enrolling and following subjects, and 2 months completing the data analysis.

5.0 Study Assessment

Case Report Forms (CRFs) and Data Clarification Forms (DCFs) will be used for data collection and query handling. The Investigator will ensure the accuracy, completeness, and timeliness of the data recorded.

All data will be entered into an Excel spreadsheet and validated to confirm integrity of data entry. Data may be transferred to an electronic data capture system at some point. When all data have been coded, validated, and signed, the database will be locked (password protected with copy saved as PDF), and available for analysis.

The study schedule of activities is shown in Table 1.

Table 1. Schedule of Activities

Procedures	Baseline (Day 0)	Follow-up (4-12 weeks)
Informed Consent	X	
Demographics & Medical History	X	
Inclusion/Exclusion Assessment	X	
Pregnancy Test (if applicable)	X	
Vitals	X	X
Physical Exam	X	X
Circumferential Measurements	X	X [^]
Bioimpedance Measurements	X	X [^]
QOL Assessment (RAND SF-36)	X	X
Mobility Assessment (PROMIS Mobility)	X	X
Symptom & Pain Intensity Assessment (PROMIS Pain Intensity, NRS Pain & Symptom Scale, Wong-Baker Faces Scale)	X	X
Randomization	X	
Training on Flexitouch Plus and/or Conservative Care*	X	
Adverse Event, Complication, & Device Observation Assessment	X	X

* If subject is unable to obtain prescribed care and complete training on use within 60 days of the Baseline visit (e.g., due to insurance coverage/scheduling delays, etc.), the subject will be considered a screen failure.
 
[^] Optional: Circumferential and bioimpedance measurements may be taken again after an in-clinic treatment with Flexitouch Plus.
		

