6.5 Randomization

If the subject meets all of the inclusion criteria and none of the exclusion criteria, they will be randomly assigned to Flexitouch Plus with conservative care or conservative care alone. Randomization codes will be generated in a permuted block design. The block size will be balanced within each block, and will maintain a 1:1 ratio between the treatment groups.

The randomization code will be distributed by sealed envelope and assigned sequentially as soon as an eligible subject completes the Baseline measurements. The appropriate staff member will obtain the next sequentially sealed randomization envelope and open it while the subject is present.

The randomization assignment cannot be changed or chosen by the subject or the investigator. The randomization envelope, as well as evidence of treatment group assignment, should be placed in the subject's binder.

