6.10 Treatment

Following randomization, collection of measurements, and the completion of questionnaires, patients will be trained on the conservative care prescribed by the investigator (or designee).

Patients randomized to the Flexitouch Plus will obtain a device through standard commercial means (via self-pay, patient assistance, or insurance programs). The standard prescription of ‘Full Leg and Core (L1)’ with daily simultaneous bilateral lower extremity treatment (~60 minutes) at normal pressure levels will be used unless alternate programming is selected by the investigator. Alternate programming (e.g., twice daily, high pressure, additional supplemental lower leg program, etc.) may be used at the investigators discretion if a subject reports inadequate control of lymphedema symptoms prior to the next study visit. While alternate programming is not expected to be necessary, it is important subjects have access to the best care possible at all times in a “real world” study.

Once the prescription is submitted/processed at the Baseline visit, device shipment and training on device use must take place within 60 days or the subject will not be enrolled in the study.

At the Follow-up visit, some or all subjects may receive an in-clinic treatment with Flexitouch Plus after the Follow-up data collection is complete. Additional circumferential (including 4 sites on each leg, 1 site at the hips, and 1 site at the waist using a Gulick II tape measure) and bioimpedance (including whole body ECW/TBW ratio, as well as segmental ratios for the Right/Left Arm, Right/Left Leg, and Trunk) measurements may be collected and recorded immediately after completion of the in-clinic Flexitouch Plus treatment.

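### Women randomised on Day 0 who do not obtain care within 60 days are reclassified as never having entered the trial, with no Follow-up or by-arm count planned for them

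*Combined protocol and SAP*

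**What the plan says.** - **Randomisation.** Table 1 (Section 5.0) marks randomisation under Baseline, Day 0. Section 6.5 says "If the subject meets all of the inclusion criteria and none of the exclusion criteria, they will be randomly assigned", and that the code is "assigned sequentially as soon as an eligible subject completes the Baseline measurements". It adds: "The randomization envelope, as well as evidence of treatment group assignment, should be placed in" her binder.
- **Obtaining care.** This follows allocation. Section 6.10: "Patients randomized to the Flexitouch Plus will obtain a device through standard commercial means".
- **The 60-day rule.** The Table 1 footnote says that if a subject cannot obtain prescribed care and complete training "within 60 days of the Baseline visit (e.g., due to insurance coverage/scheduling delays, etc.), the subject will be considered a screen failure". Section 6.10 says "device shipment and training on device use must take place within 60 days or the subject will not be enrolled in the study".
- **Enrolment and eligibility.** Section 4.3: "Subjects will be considered enrolled in the study once the Informed Consent Form is signed and eligibility criteria are met". The same section classes anyone who fails the criteria as a screen failure. Inclusion criterion 4 (Section 4.2.1) reads "Able to access (via self-pay, patient assistance, or insurance programs) prescribed care within 60 days of Baseline visit".
- **Analysis.** Section 13.2 summarises subjects who have data for the variable concerned. It names no all-randomised set, plans no imputation, and does not plan explicit missing-data counts for all variables; readers are to infer them from differing sample sizes. The between-group ANCOVA is secondary there, and Section 3.0 lists between-group comparison as exploratory.

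**The concern.** Whether a woman obtains her care is learned only after her arm is known, and it may depend on that arm. The footnote covers both arms. The shipment-and-training deadline in Section 6.10 concerns only the device, while Section 2.3.2 leaves the content of conservative care uncontrolled, so failing to obtain it is harder to define. More removals from the device arm are therefore plausible. That is an inference; the documents give no rates.

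The between-arm comparison is the one that needs randomisation, and it would rest on women selected after allocation. The within-group estimates would describe only women who obtained care. That is close to the Section 3.0 objective of device use, so for them the issue is stating scope, not plainly a bias. Reading missingness from differing sample sizes also fails here, because a woman dropped from every table as a screen failure changes no sample size.

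**Working it through.** **1. Can the passages be read consistently?** Criterion 4 has two readings.

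| Reading of criterion 4 | Sections that agree | Conflict left |
|---|---|---|
| Judged on Day 0, as expected access | 4.2.1, 4.3, 6.5 | Table 1 footnote and 6.10 remove a woman who was eligible, enrolled and randomised |
| Settled by what happens in 60 days | 4.2.1, 4.3, Table 1 footnote, 6.10 | 6.5 randomises only eligible subjects, but eligibility is not yet known on Day 0 |

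Under both readings a woman is removed after allocation.

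**2. Does another provision cover her?**
- Section 7.1 asks withdrawn subjects to return. Its reasons are withdrawn consent, an adverse event and investigator discretion; not obtaining care is not named.
- Section 7.2 requires an exit form for all subjects, but does not say whether a relabelled woman still counts as one.
- The screening log (4.3) and the envelope in the binder (6.5) would let a count be rebuilt. None is planned.
- Section 13.1 replaces 3 subjects per arm who do not complete. Whether she is among them is not stated.

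**3. The plan's own figure.** The plan gives no figure for this event. Its sample-size figure is 15 subjects (30 legs) per group for a half-width of about 0.40 SD. With 30 legs taken as independent, 1.96/√30 = 0.358 and t(0.975, 29)/√30 = 0.373, consistent with the target. With 15 subjects, the t-based value is 0.554. Subjects are the randomised units, so step 5 uses subjects.

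**4. Size of the shift.** Let p and q be the fractions removed from the device and control arms. Let d1 and d0 be the mean of retained minus removed women in each arm, in residual SD. The all-randomised mean in the device arm is (1 − p) × retained + p × removed, so retained minus all-randomised is p × d1. Hence:

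between-arm shift = p × d1 − q × d0

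| p | q | d1 | d0 | Shift (SD) |
|---|---|---|---|---|
| 10% | 0 | 0.5 | – | 0.05 |
| 20% | 0 | 0.5 | – | 0.10 |
| 20% | 20% | 0.5 | 0 | 0.10 |
| 20% | 20% | 0.5 | 0.5 | 0 |
| 30% | 0 | 1.0 | – | 0.30 |

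All inputs are assumed. Equal removal rates do not by themselves protect the comparison (third row). The sign reverses if the removed women would have done better.

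**5. Against the precision available.** With 15 per arm and 27 degrees of freedom for the ANCOVA, the 95% half-width is t(0.975, 27) × √(2/15) = 0.749 SD. Then 0.05/0.749 = 6.7%, 0.10/0.749 = 13.3% and 0.30/0.749 = 40%.

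**6. Would it happen at all?** With 15 + 3 = 18 allocated to the device and an assumed non-access rate f, the chance that at least one is relabelled is 1 − (1 − f)^18: 0.60 at 5%, 0.85 at 10% and 0.98 at 20%.

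**The case against.** The strongest defence is that the 60-day rule is an eligibility rule. If criterion 4 is settled by the outcome, a woman without access never met it, and Section 4.3 then correctly calls her a screen failure. That removes the conflict with Section 4.3. It leaves the conflict with Section 6.5, and it leaves the removal after allocation.

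Second, Section 7.1 lets the investigator withdraw subjects for unspecified reasons, Section 7.2 asks for an exit form for everyone, and Section 13.2 allows later analyses of missing data. These might be applied to her. Whether they would be is unclear, and the last is optional, so none secures her Follow-up or a count.

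Third, the study is exploratory, its primary analyses are within group, and the examples mostly give small shifts. This stands and limits the severity. The examples illustrate; they do not bound the shift.

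Fourth, an all-randomised analysis dilutes the estimate of device use, and a woman who never obtains care may have no visit date if Follow-up is counted from training. Both points are fair, and the fix has to deal with them.

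**Conclusion.** The concern holds. Followed as written, the rules exclude randomised women from the between-arm ANCOVA for an event up to 60 days after allocation, and the planned tables would not show how many or from which arm. This should be fixed, but it does not undermine the within-group aim.

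The sequence of events rests on the text alone. The harm rests on assumptions: at 10% to 20% removal from the device arm only and a 0.5 SD difference, the shift is 0.05 to 0.10 SD; it is zero when the two arms' terms are equal, and 0.30 SD at 30% and 1 SD. The 0.10 SD figure is small beside a 0.75 SD half-width. The loss of accounting does not depend on those assumptions.

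**What to change.** 1. Reconcile Sections 4.2.1, 4.3, 6.5, 6.10 and the Table 1 footnote so that screen failure and non-enrolment apply only before randomisation. After it, record the event as prescribed care not obtained within 60 days. State whether criterion 4 is a Day 0 judgement of expected access.
2. Add to Section 13.2: *Between-arm analyses include all randomised subjects with Follow-up data, in the arm assigned. Follow-up is sought whether or not prescribed care was obtained. Subjects who obtained it form a secondary set.* This fits the no-imputation rule. State that within-group estimates apply to the women who contribute to them.
3. Report by arm the numbers randomised, not obtaining care within 60 days, lost to Follow-up and analysed, using the envelopes, screening log and exit forms.
4. Keep replaced subjects (Section 13.1) in that account.

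The sponsor must first reconcile Follow-up timing: 3–4 weeks of use in Section 2.1, 4–12 weeks in Table 1, and a 30-day measurement in Section 13.2. Whatever is settled has to define a visit date for a woman who never obtains care. If the Table 1 window runs from Baseline, a woman trained on day 60 has at most 12 × 7 − 60 = 24 days of use; that lies within 3–4 weeks, but shows that the anchor matters. No anchor is proposed here, and the 60-day limit is left as it is.

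**Cost.** Wording in the sections named, one disposition table from records already kept, and one Follow-up visit for each woman now dropped. If 20% of the device arm lack the device and gain none of its benefit (assumed), the all-randomised estimate is 1 − 0.20 = 80% of the effect in users; the secondary set addresses that. Women who do not return stay missing, but the by-arm table makes them visible.
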